6.3. Measures to Minimize Bias: Randomization and Blinding

As this is an open study, blinding procedures are not applicable. Participants will be assigned to same intervention.

6.4. Study Intervention Compliance

The first dose of ibrutinib will be administered at the study site on Week 1 Day 1 and subsequent dosing will occur on an outpatient basis except for PK sampling day on Week 4 Day 1. The amount of ibrutinib dispensed will be recorded and compared with the amount returned. Compliance will be assessed by direct questioning and counting returned capsules during the site visits and documented in the source documents and eCRF. Deviation(s) from the prescribed dosage regimen should be recorded in the eCRF.

Participants will receive instructions on compliance with ibrutinib administration at the screening visit. During the study, the investigator or designated study-site personnel will be responsible for providing additional instruction to reeducate any participant who is not compliant with taking ibrutinib. Participants will use an application on the provisioned smartphone/tablet to confirm ibrutinib administration.

Rituximab will be administered as an IV infusion by qualified study-site personnel and the details of each administration will be recorded in the eCRF (including date, start and stop times of the IV infusion, and volume infused).

Study-site personnel will maintain a log of all rituximab administered. The date and time of each dose administered in the clinic will be recorded in the source documents and recorded in the eCRF.

6.5. Concomitant Therapy

Relevant concomitant therapies must be recorded throughout the study beginning with the time of written informed consent to 30 days after the last dose of ibrutinib or prior to the start of a new anticancer treatment, whichever is earlier.

The sponsor must be notified in advance (or as soon as possible thereafter) of any instances in which prohibited therapies are administered.

6.5.1. Permitted Concomitant Medications

Supportive medications in accordance with standard practice (such as for emesis, diarrhea, etc) are permitted. Use of granulocyte colony-stimulating factors or erythropoietin growth factors is permitted per institutional policy. Transfusions may be given in accordance with institutional policy.

Short courses (≤ 14 days) of steroid treatment for non-WM-related medical reasons (eg, joint inflammation, asthma exacerbation, rash, antiemetic use and infusion reactions) at doses that do not exceed 100 mg per day of prednisolone or equivalent are permitted. In addition, for participants with chronic medical conditions, continuous administration of up to 20 mg per day of prednisolone or equivalent is permitted for the treatment of this medical condition where no acceptable therapeutic alternative is available.

6.5.2. Medications to be Used with Caution

6.5.2.1. Drugs That may Alter Ibrutinib Plasma Concentrations

Ibrutinib is metabolized primarily by CYP3A. Avoid coadministration with strong or moderate CYP3A inhibitors and consider alternative agents with less CYP3A inhibition. If a strong CYP3A inhibitor must be used, consider reducing the ibrutinib dose to 140 mg or withhold treatment temporarily. Participants should be monitored for signs of ibrutinib toxicity. If the benefit outweighs the risk and a moderate CYP3A inhibitor must be used, monitor participant for toxicity and follow dose modification guidance as needed. Avoid grapefruit and Seville oranges during ibrutinib treatment, as these contain moderate inhibitors of CYP3A.

Avoid concomitant use of strong CYP3A inducers (eg, carbamazepine, rifampin, phenytoin, and St. John's Wort). Consider alternative agents with less CYP3A induction.

A list of common CYP3A inhibitors and inducers is provided in Section 10.7, Appendix 7; a comprehensive list of inhibitors, inducers, and substrates may be found at <http://medicine.iupui.edu/clinpharm/ddis/table.aspx>. This website is continually revised and should be checked frequently for updates.

6.5.2.2. Drugs That may Have Their Plasma Concentrations Altered by Ibrutinib

In vitro studies indicated that ibrutinib is a weak reversible inhibitor toward CYP2B6, CYP2C8, CYP2C9, CYP2C19, CYP2D6, and CYP3A4/5 and does not display time-dependent CYP450 inhibition. The dihydrodiol metabolite of ibrutinib is a weak inhibitor toward CYP2B6, CYP2C8, CYP2C9, and CYP2D6. Both ibrutinib and the dihydrodiol metabolite are weak inducers of CYP450 isoenzymes in vitro. Therefore, it is unlikely that ibrutinib treatment results in any clinically relevant drug-drug interactions (DDIs) with drugs that may be metabolized by the CYP450 enzymes.

Ibrutinib is a mild inhibitor of P-glycoprotein (P-gp) and breast cancer resistance protein (BCRP). Ibrutinib is not expected to have systemic drug-drug interactions with P-gp substrates. However, it cannot be excluded that ibrutinib could inhibit intestinal P-gp after a therapeutic dose. There are no clinical data available. Therefore, to avoid a potential interaction in the gastrointestinal tract, narrow therapeutic range P-gp substrates such as digoxin, should be taken at least 6 hours before or after ibrutinib.

6.5.2.3. Concomitant Use of Antiplatelet Agents and Anticoagulants

Supplements such as fish oil and vitamin E preparations should be avoided. Use ibrutinib with caution in participants requiring anticoagulants or medications that inhibit platelet function. Participants with congenital bleeding diathesis have not been studied.

Participants requiring the initiation of therapeutic anticoagulation therapy (eg, atrial fibrillation), consider the risks and benefits of continuing ibrutinib treatment. If therapeutic anticoagulation is clinically indicated, treatment with ibrutinib should be held and not be restarted until the participant is clinically stable and has no signs of bleeding. No dose reduction is required when ibrutinib is restarted. Participants should be observed closely for signs and symptoms of bleeding.

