6.1.1.3. Dose Modification for Adverse Reactions

The dose of ibrutinib should be modified according to the dose modification guidance in [Table 2](#) or [Table 3](#) if any of the following drug-related toxicities occur:

Refer to [Table 2](#)

- Grade 3 or greater neutropenia with infection or fever

- Grade 4 ANC (<500/ μ L) for >7 days
- Grade 3 thrombocytopenia (platelets <50,000/ μ L) in the presence of \geq Grade 2 bleeding events
- Grade 4 thrombocytopenia (platelets <25,000/ μ L)
- Grade 3 or 4 nausea, vomiting, or diarrhea if persistent, despite optimal antiemetic and/or antidiarrheal therapy
- Any other Grade 4 or unmanageable Grade 3 toxicity attributed to ibrutinib (except events specified in [Table 3](#))

Refer to [Table 3](#)

- Grade 2 or higher cardiac failure and Grade 3 or higher cardiac arrhythmias

For Grade 3 or 4 atrial fibrillation or persistent atrial fibrillation of any grade, consider the risks and benefits of ibrutinib treatment. If clinically indicated, the use of anticoagulants or antiplatelet agents may be considered for the thromboprophylaxis of atrial fibrillation (Section [6.5.2.3](#)).

Table 2: Ibrutinib Dose Modifications for Events not Specified in [Table 3](#)

Occurrence	Action to be Taken
First	Withhold ibrutinib until recovery to Grade \leq 1 or baseline; may restart at original dose level ^a
Second	Withhold ibrutinib until recovery to Grade \leq 1 or baseline; may restart at 1 dose level lower (ie, 280 mg/day / 2 capsules)
Third	Withhold ibrutinib until recovery to Grade \leq 1 or baseline; may restart at 1 dose level lower (ie, 140 mg/day / 1 capsule)
Fourth	Discontinue ibrutinib ^b

^a When resuming treatment, restart at the same or lower dose based on benefit risk evaluation. If the toxicity reoccurs, reduce daily dose by 140 mg.

^b If the oral ibrutinib is discontinued for toxicity, participant will end the treatment phase of the study.

Table 3: Ibrutinib Dose Modifications for Cardiac Failure or Cardiac Arrhythmias

Events	Occurrence	Action to be Taken
Grade 2 cardiac failure	First	Withhold ibrutinib until recovery to Grade \leq 1 or baseline; restart at 1 dose level lower (ie, 280 mg/day / 2 capsules)
	Second	Withhold ibrutinib until recovery to Grade \leq 1 or baseline; restart at 1 dose level lower (ie, 140 mg/day / 1 capsule)
	Third	Discontinue ibrutinib ^b

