Grade 3 cardiac arrhythmias	First	Withhold ibrutinib until recovery to Grade \leq 1 or baseline; restart at 1 dose level lower (ie, 280 mg/day / 2 capsules) ^a
	Second	Discontinue ibrutinib ^b
Grade 3 or 4 cardiac failure	First	Discontinue ibrutinib ^b
Grade 4 cardiac arrhythmias		

^a Evaluate the benefit-risk before resuming treatment.

^b If the oral ibrutinib is discontinued for toxicity, participant will end the treatment phase of the study.

Refer to Section [6.5.2.1](#) for guidelines for management of ibrutinib in participants who require treatment with a CYP3A inhibitor.

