6.1.1.4. Dose Modification for Hepatic Impaired Participants

Ibrutinib is metabolized in the liver. For participants who develop mild liver impairment while on study (Child-Pugh class A), the recommended dose reduction for ibrutinib is to a level of 280 mg daily (2 capsules). Participants who develop moderate or severe hepatic impairment (Child-Pugh class B or C) must hold ibrutinib until resolved to mild impairment (Child-Pugh class A) or better, and could be retreated according to resolved hepatic conditions (ie, 280 mg for mild impairment). Monitor participants for signs of toxicity and follow dose modification guidance as needed (refer to Section 6.1.1.3). Child-Pugh Score is provided in Section 10.6, Appendix 6.

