6.6. Dose Modification

Any dose/dosage adjustment should be overseen by medically-qualified study-site personnel (principal or subinvestigator unless an immediate safety risk appears to be present).

This protocol allows some alteration from the currently outlined dose schedule, but the maximum daily dose and/or (predicted) maximum/cumulative exposure will not exceed dose specified in this protocol.

Details for dose modifications are described in Sections [6.1.1.3](#) and [6.1.1.4](#) for ibrutinib and in Section [6.1.2.4](#) for rituximab.

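### Section 6.5.2.3 waives dose reduction at ibrutinib restart without exception, while Table 3 requires 280 mg/day after a first drug-related Grade 3 arrhythmia

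*Protocol*

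**What the plan says.** Two parts of the protocol set the ibrutinib restart dose.

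**Section 6.5.2.3 (antiplatelet agents and anticoagulants).** The rule applies when therapeutic anticoagulation has to be started, and atrial fibrillation is its only example. Ibrutinib is held until the participant is clinically stable and not bleeding. Then: "No dose reduction is required when ibrutinib is restarted". The section names no exception and does not mention Table 3.

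**Section 6.1.1.3 and Table 3 (dose modification for adverse reactions).** The section says the dose should be modified under Table 2 or Table 3 for listed drug-related toxicities. Those sent to Table 3 are "Grade 2 or higher cardiac failure and Grade 3 or higher cardiac arrhythmias". For a first Grade 3 arrhythmia, Table 3 says to withhold ibrutinib until recovery to Grade 1 or less, or baseline, and then "restart at 1 dose level lower (ie, 280 mg/day / 2 capsules"). A footnote asks for a benefit-risk evaluation before resuming.

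**The link between them.** Straight after listing the Table 3 events, section 6.1.1.3 takes up Grade 3 or 4 atrial fibrillation and persistent atrial fibrillation of any grade. It says that, if clinically indicated, "the use of anticoagulants or antiplatelet agents may be considered for the thromboprophylaxis of atrial fibrillation", and refers to section 6.5.2.3.

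**The concern.** A first drug-related Grade 3 atrial fibrillation that needs anticoagulation falls under both rules. One says that no reduction is required at restart; the other requires one. An investigator who follows the pointer from 6.1.1.3 arrives at the unqualified sentence in 6.5.2.3.

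A site that takes that sentence literally would resume at the full dose, contrary to Table 3. The participant would have just had a Grade 3 arrhythmia and started an anticoagulant, and section 2.3.1 says anticoagulants given with ibrutinib raise the risk of major bleeding. This is a question of participant safety and consistent dosing. It has no bearing on the primary analysis.

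**Working it through.** The protocol states no figure to reproduce. The check sets the rules side by side and then does the dose arithmetic.

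**1. Where the rules meet.** Take a participant on 420 mg/day (section 6.1) who starts therapeutic anticoagulation because of an arrhythmia.

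| Event | Table 3 | Section 6.5.2.3 | Agree? |
|---|---|---|---|
| Grade 1 or 2 arrhythmia, or one that is not drug-related | Does not apply | No reduction required | Yes |
| First drug-related Grade 3 | Restart at 280 mg/day | No reduction required | No |
| Second drug-related Grade 3 | Discontinue | No restart arises | Yes |
| Drug-related Grade 4 | Discontinue | No restart arises | Yes |

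Only the second row conflicts. It arises when anticoagulation is needed and ibrutinib is resumed.

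**2. Size of the difference.**
- One dose level is one 140 mg capsule: 420 − 140 = 280 mg/day, which matches Table 3.
- Literal 6.5.2.3 against Table 3: 420 − 280 = 140 mg/day.
- Ratio: 420 / 280 = 1.50, so the literal dose is 50% above the Table 3 dose.

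**3. Is the Table 3 reduction optional?** No. Table 2 says that ibrutinib may restart; the Table 3 entry is a direct instruction to restart one level lower. The footnote adds a check before resuming and does not waive the reduction.

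**4. Do the release criteria conflict?** No. Recovery to Grade 1 or baseline (Table 3) and clinical stability without bleeding (6.5.2.3) can both be required. Only the restart dose is at issue.

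**5. Does other text settle it?**
- Section 6.6 says "Details for dose modifications are described in Sections" 6.1.1.3 and 6.1.1.4 for ibrutinib. That suggests Table 3 is meant to govern, but it is a pointer and sets no order of precedence.
- Section 6.5.2.1, on moderate CYP3A inhibitors, says to "monitor participant for toxicity and follow dose modification guidance as needed". Section 6.1.1.4, on hepatic impairment, says to "follow dose modification guidance as needed". Section 6.5.2.3 has no such deferral.
- The note under Table 3 refers to section 6.5.2.1 "for guidelines for management of ibrutinib in participants who require treatment with a CYP3A inhibitor". It has no matching reference to 6.5.2.3.

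**The case against.** The strongest reply is that the sentence answers a narrower question. It sits among the concomitant-medication rules and follows a hold triggered by an anticoagulant, so it says only that this hold costs no dose level. Saying that a reduction is not required does not forbid one. A site that restarts at 280 mg/day breaches neither text, and 6.5.2.3 never states 420 mg. Section 6.6 omits 6.5.2.3 from its list of dose-modification sections, and section 2.3.1 says to follow the dose modification guidelines for arrhythmias that persist. The pointer in 6.1.1.3 concerns whether anticoagulants may be used, not the restart dose, and a reader who follows it has just been told that Grade 3 arrhythmias go to Table 3.

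Much of this stands. It is the likely intent, and under it 280 mg/day satisfies both sections. The sentence is also correct for atrial fibrillation outside Table 3 and for other reasons to anticoagulate. The comparison with 6.5.2.1 and 6.1.1.4 is suggestive only, since those sections concern altered ibrutinib metabolism. The protocol does not say that a lower dose reduces bleeding, so the bleeding risk describes the setting and is not a measured harm of the higher dose.

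The wording remains unresolved, however. The sentence is not limited to anticoagulation alone, and its one example is itself an arrhythmia. The instruction in 2.3.1 is background text, covers only persistent arrhythmias and does not mention restarting after anticoagulation. The reader has to infer the right dose.

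**Conclusion.** The concern holds: section 6.5.2.3 is wrong as written for one case. For a first drug-related Grade 3 arrhythmia that needs therapeutic anticoagulation and after which ibrutinib is resumed, its literal text permits 420 mg/day where Table 3 requires 280 mg/day. This assumes that the participant was on the full dose when the event occurred.

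The protocol gives no rate for this sequence of events, so the number affected is unknown and may be zero among the 14 planned participants. The point should be corrected because sites dose from this text, but it has no consequence for the ORR test, the sample size or the analysis sets.

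**What to change.** Replace the sentence in section 6.5.2.3 with:

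> *No dose reduction is required for anticoagulation alone when ibrutinib is restarted; if the event also meets Table 3, the Table 3 action, recovery criterion and restart dose apply in addition to clinical stability and absence of bleeding.*

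Under Table 3, beside the existing reference to 6.5.2.1, add a reference to 6.5.2.3 for participants who start therapeutic anticoagulation. Because the new clause refers to Table 3 as a whole, it also covers Grade 2 cardiac failure.

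The cost is one clause and one cross-reference, with no added procedures. If the sponsor already intends the narrower reading, the change only states that intent.

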6.5.3. Prohibited Concomitant Medications

Any other chemotherapy, anticancer immunotherapy, experimental therapy, or radiotherapy are prohibited while the participant is receiving ibrutinib. Corticosteroids for the treatment of the underlying disease are prohibited. The sponsor must be notified in advance (or as soon as possible thereafter) of any instances in which prohibited therapies are administered.

6.6. Dose Modification

Any dose/dosage adjustment should be overseen by medically-qualified study-site personnel (principal or subinvestigator unless an immediate safety risk appears to be present).

This protocol allows some alteration from the currently outlined dose schedule, but the maximum daily dose and/or (predicted) maximum/cumulative exposure will not exceed dose specified in this protocol.

Details for dose modifications are described in Sections [6.1.1.3](#) and [6.1.1.4](#) for ibrutinib and in Section [6.1.2.4](#) for rituximab.

6.7. Intervention After the End of the Study

Telephone contact will be made to confirm survival status including subsequent anticancer therapy and other malignancies every 12 weeks for up to study termination by the sponsor after the last dose of study intervention, unless the participant has died, is lost to follow-up, or has withdrawn consent. If the information on survival status is obtained via telephone contact, written documentation of the communication must be available for review in the source documents. If the participant has died, the date and cause of death will be collected and documented on the eCRF.

Investigators may recontact the participant to obtain long-term follow-up information regarding the participant's safety or survival status as noted in the ICF (refer to Informed Consent in Section [10.3](#), Appendix 3, Regulatory, Ethical, and Study Oversight Considerations).

Participants will be instructed that study intervention will not be made available to them after they have completed/discontinued study intervention and that they should return to their primary physician to determine standard of care.

7. DISCONTINUATION OF STUDY INTERVENTION AND PARTICIPANT DISCONTINUATION/WITHDRAWAL

Discontinuation of study intervention does not result in automatic withdrawal of the participant from the study. Participants who discontinue study intervention should continue to have assessments performed as specified in the [Schedule of Activities \(SoA\)](#) or disease evaluations prior to progression.

7.1. Discontinuation of Study Intervention

A participant's study intervention must be discontinued if:

- The participant withdraws consent to receive study intervention
- The investigator believes that for safety reasons or tolerability reasons (eg, AE) it is in the best interest of the participant to discontinue study intervention
- The investigator's decision (such as significant noncompliance with study intervention administration, significant protocol deviation, or best interest of the participant)
- The participant with confirmed PD

If the participant becomes pregnant, the study treatment should be suspended and the Medical Monitor should be contacted as soon as possible to discuss study treatment options. Refer to Section [8.6.4](#), Pregnancy and Section [10.5](#), Appendix 5, Contraceptive and Barrier Guidance and Collection of Pregnancy Information.

If a participant discontinues study intervention for any reason before the end of the study, then the end-of-intervention and postintervention assessments should be obtained and scheduled assessments per Section [1.3](#) or disease evaluations prior to progression should be continued. Study intervention assigned to the participant who discontinued study intervention may not be assigned to another participant. Additional participants will not be entered.

7.2. Participant Discontinuation/Withdrawal From the Study

A participant will be withdrawn from the study for any of the following reasons:

- Lost to follow-up
- Withdrawal of consent
- Death
- Sponsor discontinues the study

When a participant withdraws before study completion, the reason for withdrawal is to be documented in the eCRF and in the source document. If the reason for withdrawal from the study is withdrawal of consent, then no additional assessments are allowed.

Withdrawal of Consent

A participant declining to return for scheduled visits does not necessarily constitute withdrawal of consent. Alternate follow-up mechanisms that the participant agreed to when signing the consent

form apply (eg, consult with family members, contacting the participant's other physicians, medical records, database searches, use of locator agencies at study completion,) as local regulations permit.

Withdrawal of consent should be an infrequent occurrence in clinical studies, therefore, prior to the start of the study the sponsor and the investigator should discuss and reach a clear understanding of what constitutes withdrawal of consent in the context of the available reduced follow-up mechanisms listed.

Study Completion Definition

A participant who is in the treatment period at the time, when marketing approval is received, will discontinue the study intervention and will complete an EOT visit before the study end. A participant who is in the follow-up period at this time will stop the further follow-up. Both participants will be considered to have completed the study.

7.2.1. Withdrawal From the Use of Research Samples

Withdrawal From the Use of Samples in Future Research

The participant may withdraw consent for use of samples for research (refer to Long-Term Retention of Samples for Additional Future Research in Section 10.3, Appendix 3, Regulatory, Ethical, and Study Oversight Considerations). In such a case, samples will be destroyed after they are no longer needed for the clinical study. Details of the sample retention for research are presented in the main ICF.

7.3. Lost to Follow-up

To reduce the chances of a participant being deemed lost to follow-up, prior to enrollment attempts should be made to obtain contact information from each participant, eg, home, work, and mobile telephone numbers and email addresses for both the participant as well as appropriate family members.

A participant will be considered lost to follow-up if he or she repeatedly fails to return for scheduled visits and is unable to be contacted by the study site. A participant cannot be deemed lost to follow-up until all reasonable efforts made by the study-site personnel to contact the participant are deemed futile. The following actions must be taken if a participant fails to return to the study site for a required study visit:

- The study-site personnel must attempt to contact the participant to reschedule the missed visit as soon as possible, to counsel the participant on the importance of maintaining the assigned visit schedule, to ascertain whether the participant wishes to or should continue in the study.
- Before a participant is deemed lost to follow-up, the investigator or designee must make every reasonable effort to regain contact with the participant. These contact attempts should be documented in the participant's medical records.
- Should the participant continue to be unreachable, they will be considered to have withdrawn from the study.

